12.3.5 Secondary efficacy variables

In cases where observed primary feeding method during the treatment period (formula / any maternal breast milk) differs from the feeding method at time of randomization, the observed primary feeding method will be used for analysis.

Time to first weaning

Time to first weaning is defined as the number of hours from start of the treatment until the first dose reduction.

An ANCOVA model based on log-transformed data will be performed to test the treatment effect as time to first weaning (hours).

The model will include treatment (CHF6563 and morphine) as a fixed effect and covariates for primary feeding method (formula/ any maternal breast- milk), Maternal primary opioid use (buprenorphine/ methadone / other), and maternal use of benzodiazepines, antidepressants or gabapentin (polypharmacy [yes/no]). The adjusted geometric mean in each treatment group, the adjusted ratio of geometric means between treatments, together with its 95% CI and associated p-value will be estimated by the model.

Requirement for adjunctive drug therapy (phenobarbital) for signs of NOWS

Only adjunctive drug therapy during the treatment period will be considered. Odds ratios and corresponding 95% CIs will be presented, based on logistic regression, adjusting for primary feeding method (formula / any maternal breast milk), maternal primary opioid use (buprenorphine /methadone / other), and maternal use of benzodiazepines, antidepressants or gabapentin (polypharmacy [yes/no]).

Total hours of treatment with adjunctive therapy (phenobarbital)

Total hours of treatment with adjunctive therapy is defined as the sum of time on each occasion when adjunctive therapy is required (since babies may require adjunctive therapy on separate occasions). For each

Clinical Study Code No.: CLI-06563AA1-02	Version No.: 6.0
IND No.: 131,339	Date: 18 March 2021

occasion requiring adjunctive therapy, the time of treatment is defined as the time of first dose until the last dose.

Total hours of treatment with adjunctive therapy will be analysed using an ANCOVA model. The model will include treatment (CHF6563 and morphine) as a fixed effect and primary feeding method (formula/any maternal breast- milk), maternal primary opioid use (buprenorphine/ methadone/ other), and maternal use of benzodiazepines, antidepressants or gabapentin (polypharmacy [yes/no]) as covariates. Babies not requiring adjunctive therapy will be included as 0 hours.

Requirement for rescue doses (CHF6563 or morphine)

Only rescue doses during the treatment period will be considered. Odds ratios and corresponding 95% CIs will be presented, based on logistic regression, adjusting for primary feeding method (formula / any maternal breast milk), maternal primary opioid use (buprenorphine /methadone / other), and maternal use of benzodiazepines, antidepressants or gabapentin (polypharmacy [yes/no]).

Number of rescue doses administered

Number of rescue doses administered will be analyzed using an ANCOVA model. The model will include treatment (CHF6563 and morphine) as a fixed effect and primary feeding method (formula / any maternal breast milk), maternal primary opioid use (buprenorphine / methadone / other), and maternal use of benzodiazepines, antidepressants or gabapentin (polypharmacy [yes/no]) as covariates. Babies not requiring rescue dose(s) will be included with a value of 0.

Percentage of total amount of active study drug which is from rescue doses

The percentage of total amount of active study drug which is from rescue doses will be analyzed using an ANCOVA model. The model will include treatment (CHF6563 and morphine) as a fixed effect and primary feeding method (formula / any maternal breast milk), maternal primary opioid use (buprenorphine / methadone / other), and maternal use of benzodiazepines, antidepressants or gabapentin (polypharmacy [yes/no]) as covariates. Babies not requiring rescue dose(s) of active study drug will be included with a value of 0.

Length of opioid related hospital stay

Length of opioid related hospital stay is defined as number of days from day of birth until 48 hours after the final dose of drug treatment for NOWS.

Length of opioid related hospital stay (days) will be analyzed using an ANCOVA model based on log-transformed data. will be performed to test the treatment effect as length of opioid-related hospital stay (days).

The model will include treatment (CHF6563 and morphine) as a fixed effect and primary feeding method (formula / any maternal breast milk), maternal primary opioid use (buprenorphine / methadone / other), and maternal use of benzodiazepines, antidepressants or gabapentin (polypharmacy [yes/no]) as covariates. The adjusted mean in each treatment group, the adjusted ratio of geometric means between treatments, its 95% CIs and associated p-value will be estimated by the model.

Incidence of relapse of Nows, defined as experiencing recurrence of significant signs of withdrawal

Odds ratios and corresponding 95% CIs will be presented, based on logistic regression, adjusting for primary feeding method (formula/ any maternal breast milk), maternal primary opioid use (buprenorphine /methadone / other), and maternal use of benzodiazepines, antidepressants or gabapentin (polypharmacy [yes/no]). The odds ratio of incidence between treatment groups will be presented together with the 95% CI and corresponding p-value.

Incidence of readmissions, defined as readmission to hospital for Nows relapse

Odds ratios and corresponding 95% CIs will be presented, based on logistic regression, adjusting for primary feeding method (formula/any maternal breast milk), maternal primary opioid use (buprenorphine

Clinical Study Code No.: CLI-06563AA1-02	Version No.: 6.0
IND No.: 131,339	Date: 18 March 2021

/methadone / other), and maternal use of benzodiazepines, antidepressants or gabapentin (polypharmacy [yes/no]). The odds ratio of incidence between treatment groups will be presented together with the 95% CI and corresponding p-value.

12.3.6 Pharmacokinetic variables

The relative low number of blood samples per baby, the opportunistic sampling strategy and the continuous variation of the administered dose prevent the application of standard non-compartmental analysis for the characterization of CHF6563 pharmacokinetics in the neonate population.

Instead, a population pharmacokinetic modelling approach will be applied. A separate analysis plan and report will be produced.

12.3.7 Safety variables

Adverse Events

Safety analysis will be based on Safety population. All adverse events starting on or after the time of first study drug intake will be classified as treatment emergent adverse event (TEAE). Any adverse events started after the informed consent signature and before the time of first study drug intake will be classified as pre-treatment adverse events.

The number of babies who experienced at least one TEAE, drug-related TEAE, serious TEAE, serious related TEAE, TEAE leading to study discontinuation, TEAE leading to death, and peri-dosing TEAEs will be summarized by treatment arm. Summaries will be presented overall (number and percentage of babies having at least one event, total number of events) and by system organ class and preferred term (number and percentage of babies having at least one occurrence of that event).

All adverse events will be listed.

Pre-treatment adverse event will be listed only.

The peri-dosing AEs are defined as adverse events occurring during or shortly after administration of study treatment, i.e. within 10 minutes from the start of study drug administration.

Vital signs

Vital signs will be summarized at each planned time point by means of descriptive statistics. At each timepoint when vital signs are collected, mean, min, max and standard deviation of the observed values and change from baseline will be presented, in addition to being listed.

Laboratory data

Sites will use local labs to obtain liver enzymes analysis-function testing. When consistent with site clinical practice, sites will use local labs to collect hematology and blood chemistry. The laboratory values and the change from baseline for continuous laboratory parameters will be summarized by descriptive statistics at each planned time point. All laboratory data will be listed with abnormal values flagged.

Head circumference (and percentile) and body weight (and percentile)

Head circumference (and percentile) and body weight (and percentile) and their corresponding changes from baseline will be summarized using descriptive statistics at each planned time point.

Additional Safety Variables

The following parameters collected only at the end of the treatment period will be listed only:

- Neurological and behavioral assessment

Analysis of safety variables collected at the 18-month follow up visit will be described in the SAP.

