6.5 Treatment allocation

Babies will be assigned in a 2:1 ratio to either CHF6563 or morphine. Randomization will be stratified according to the following variables, using a dynamic randomization algorithm (i.e. minimization) to balance treatment arms with respect to stratification factor levels, while maintaining an overall treatment balance:

- Neonate's feeding status at time of randomization (formula/ any maternal breast- milk [including combination of breast milk and formula])
- Maternal primary opioid use (buprenorphine/methadone/other)
- Maternal concurrent use of benzodiazepines, antidepressants or gabapentin (polypharmacy [yes/no]); please refer to [APPENDIX 3 – List of PSYCHOTROPIC DRUGS](#) for the list of drugs to be checked.

Clinical Study Code No.: CLI-06563AA1-02	Version No.: 6.0
IND No.: 131,339	Date: 18 March 2021

The minimization method is planned in order to maximize the balance of each stratification variable as well as the overall treatment balance across arms in a 2:1 ratio, considering the planned sample size [37]. This method achieves a greater level of balance across multiple stratification variables compared to a traditional stratified randomization

Babies will be centrally assigned to one of the two treatment arms on randomization through an IRT system (Interactive Response Technology, combination of voice and web response system and also referred as IVRS/IWRS).

Following 2 consecutive FNAST with a sum ≥ 12 , if all eligibility criteria except for Inclusion Criterion #5 are met, then babies will be pre-randomized in the IRT system to ensure treatment is available should Inclusion Criterion #5 be met (i.e. the sum of 3 consecutive FNAST scores ≥ 24 or a single score ≥ 12).

The IRT will allocate the patient to a certain treatment group using biased coin application of the Pocock and Simon minimization algorithm [37], and assign the study medication kit number corresponding to the babies' treatment group. IRT specifications will be fully described in a specific document. The IRT will also generate a confirmation after every IRT transaction is performed.

The patient will be identified by a unique number of six digits: the investigational site number will be the first three digits and the following three digits will be the progressive numbering of the patient within each site (e.g. 101001, 101002 etc.).

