12. STATISTICAL METHODS

12.1 Sample Size

On the basis of the results of similar studies, it was determined that a sample size of 51 babies in (17 randomized to morphine and 34 randomized to CHF6563) will provide a power of 80% to detect a difference in duration of treatment of 13 days (312 hours), assuming a common standard deviation of 15 days and a two-sided significance level of 0.05. Assuming an early withdrawal rate of 10%, a total of 57 neonates will be randomized in order to reach a total of 51 evaluable babies completing the treatment period. Based on an assumed screening failure rate of 80%. It is anticipated that approximately 285 mothers should be pre-screened to achieve 57 randomized babies.

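### Adverse events are summarised by arm without regard to time on treatment, so if CHF6563 shortens treatment, an equal daily risk will tend to show as fewer babies with events on CHF6563

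*Protocol*

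**What the plan says.** Safety and tolerability is one of two primary objectives (Protocol 2.1). Protocol 12.3.7 summarises by arm "The number of babies who experienced at least one TEAE, drug-related TEAE, serious TEAE" and further categories, as number and percentage of babies and total number of events, with tables by system organ class and preferred term. The counting window opens at first dose and has no stated end: "All adverse events starting on or after the time of first study drug intake will be classified as treatment emergent adverse event (TEAE").

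Follow-up lasts 6 weeks from each baby's final opioid dose (Protocol 3). The primary endpoint is duration of treatment (Protocol 8.1), and the sample size rests on "a difference in duration of treatment of 13 days" (Protocol 12.1). The background and rationale (Protocol 1.1 and 1.2) present CHF6563 as intended to shorten treatment, and Protocol 3 states that it needs fewer weaning steps than morphine.

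SAP v2.0 keeps one overview table of subjects, percentages and events by treatment (SAP 3.1.3). It uses subjects as the denominator for event data (SAP 5.4.1), defines a treatment phase ending 48 hours after the last dose (SAP 5.2.1), and only lists exposure (SAP 4.6.2). Neither document plans a rate per unit of exposure, a time-to-first-event analysis or a common fixed window.

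**The concern.** A baby observed for longer has more opportunity for an event to be recorded. Here the length of observation is tied to the outcome that the trial hopes to change. The 6-week follow-up does not equalise it, because it is added to each baby's own treatment time. If CHF6563 shortens treatment, its babies contribute fewer days, and both the percentage with an event and the number of events per baby will tend to be lower on CHF6563 even when the risk per day is identical.

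At stake is the reading of a primary objective. From the planned tables a reader could not tell a lower daily risk from a shorter course. Both may matter, but they are different findings.

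**Working it through.** **Inputs from the documents.** Difference in mean duration 13 days; "assuming a common standard deviation of 15 days and a two-sided significance level of 0.05"; 80% power; "17 randomized to morphine and 34 randomized to CHF6563" (Protocol 12.1); 2:1 allocation (Protocol 6.5); 38 and 19 babies randomised (Protocol outline); follow-up 6 weeks = 42 days after last dose (Protocol 3); treatment phase to last dose + 48 h (SAP 5.2.1).

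**Step 1: the plan's own figure.** For a two-sample t-test the noncentrality is 13 / (15 × √(1/17 + 1/34)) = 2.92 with 49 degrees of freedom, giving 81.6% power. At 16 and 32 babies power is 79.1%, so 51 is the smallest 2:1 size reaching 80%. 51 / 0.9 = 56.7, rounded up to 57. The figure reproduces, and it shows that 13 days is the difference the trial is powered to detect.

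**Step 2: assumptions.** The documents give no mean durations and no AE rates. Assumed: mean CHF6563 treatment 15 days; morphine 28 days (15 + 13), or 20 days (15 + 5). The 5 days is the approximate placebo tail that Protocol 3 says CHF6563 babies would otherwise face, and the only built-in gap the documents quantify. The daily AE hazard h is constant and the same in both arms: 1%, 2% or 3%.

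**Step 3: formulas.** Crude risk = 1 − exp(−h × T), where T is the window in days. Odds ratio, morphine to CHF6563 = (exp(h × T of morphine) − 1) / (exp(h × T of CHF6563) − 1).

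Example, h = 2%, first dose to end of follow-up: T = 15 + 42 = 57 and 28 + 42 = 70. 1 − exp(−1.14) = 68%; 1 − exp(−1.40) = 75%.

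**Step 4: results (CHF6563 vs morphine, no true difference in daily risk).**

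| Window | Treatment days | T | h = 1% | h = 2% | h = 3% | Odds ratio |
|---|---|---|---|---|---|---|
| First dose to end of 6-week follow-up | 15 vs 28 | 57 vs 70 | 43 vs 50% | 68 vs 75% | 82 vs 88% | 1.3–1.6 |
| Same | 15 vs 20 | 57 vs 62 | 43 vs 46% | 68 vs 71% | 82 vs 84% | 1.1–1.2 |
| Treatment phase (last dose + 48 h) | 15 vs 28 | 17 vs 30 | 16 vs 26% | 29 vs 45% | 40 vs 59% | 1.9–2.2 |

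Expected events per baby scale with T: 70 / 57 = 1.23 and 30 / 17 = 1.76 for the 15 vs 28 day case. The total number of events therefore has the same problem.

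**Step 5: sensitivity.** With the 13-day difference kept and mean CHF6563 duration varied from 10 to 25 days, the ratio of observation time runs from 1.19 to 1.25 through follow-up and from 1.48 to 2.08 in the treatment phase. With lognormal durations (SD 15 days, capped at 70 days, means 15 vs 28) and h = 2%, the crude figures are 66.9 vs 74.3% through follow-up and 26.3 vs 42.9% in the treatment phase, while the rate is 2.0 per 100 baby-days in both arms.

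**Step 6: set against chance.** With 38 and 19 babies and a proportion near 45%, the standard error of the difference is √(0.45 × 0.55 × (1/38 + 1/19)) = 14 percentage points. The tilt through follow-up at 15 vs 28 days is 6 to 7 points.

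**The case against.** The strongest reply is that risk per course is a valid measure of a regimen whose purpose is a shorter course. Fewer events because treatment ends sooner may be a real benefit, and the objective does not ask for a daily hazard. This stands. It is a reason to keep the crude percentages and not to rest between-arm statements on rates alone.

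Rates have their own weakness: one rate per arm summarises risk fairly only if the hazard is roughly constant. Doses fall during weaning, and vital signs are then collected once a day instead of with every score. If events cluster early, dividing by a longer and quieter weaning period may understate risk in the longer-treated arm. This also stands and should be stated with the table.

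The protocol's safety summaries are descriptive, with no test or interval between arms, so no formal claim is biased. That holds too, although percentages set side by side by arm invite comparison.

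Two stronger readings are tempting. A reader might infer that the trial expects morphine babies to be treated 13 days longer. The documents support only that it is powered for that difference and that CHF6563 is intended to be the shorter arm. A reader might also apply the odds ratios of about 2 to the planned TEAE table. They belong to the treatment phase. The TEAE definition has no end, so its counts include follow-up and the tilt is smaller. The larger figures are relevant to events confined to treatment, such as peri-dosing events, which Protocol 12.3.7 limits to 10 minutes from the start of a dose and which follow-up cannot dilute.

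**Conclusion.** The gap is real and its direction is foreseeable: if CHF6563 shortens treatment as intended, equal daily risk will tend to give lower crude percentages and counts on CHF6563. On the assumptions above (constant equal hazard of 1% to 3% per day, mean CHF6563 treatment 15 days), the tilt in the TEAE window as written is about 6 to 7 points for a 13-day gap and 2 to 3 points for a 5-day gap. For events restricted to the treatment phase it is about 10 to 19 points for a 13-day gap.

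The documents do not support saying that CHF6563 will look safer. At this sample size chance variation is larger than the open-window tilt, so this is a systematic lean and not a certain result. Nor do they support calling the crude percentages wrong; they answer a different question from rates.

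The point concerns the protocol's planned analysis. SAP v2.0 records that 7 babies were randomised, that the objectives are not evaluable and that no statistical analysis will be done, and it lists all adverse events and exposure. The practical effect there is negligible.

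**What to change.** In Protocol 12.3.7, keep the crude percentages and event counts and add by arm:

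- a summary of treatment-phase baby-days;
- AE rates per 100 baby-days, with numerator and denominator taken from the same window: first dose to last dose + 48 h, and separately first dose to the end of the 6-week follow-up;
- a statement that the percentages (risk per course) and the rates (risk per day) are to be interpreted together, with between-arm statements resting on neither alone;
- a note that rates assume a roughly constant hazard and may understate risk in the longer-treated arm if events cluster early.

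The treatment-phase rate needs its own event count, because the TEAE rows have no end date; it cannot be formed by dividing those rows by treatment-phase days.

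The cost is a few table columns and a short exposure summary. Dose times and event start times are already collected, and SAP 5.2.1 already defines the treatment phase. No new data and no change to the conduct of the trial are needed. Amending SAP v2.0 for 7 babies would add little.

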12.3.8 Interim analysis

A blinded sample size re-assessment (BSSR) will be performed when approximately 23-28 babies (40-50% of the planned sample size) have completed the treatment period. At this time, the overall variance based on

Clinical Study Code No.: CLI-06563AA1-02	Version No.: 6.0
IND No.: 131,339	Date: 18 March 2021

all completed patients (without knowledge or consideration of treatment arm) will be evaluated and the sample size may be increased if the variability is higher than anticipated beyond a certain threshold.

The BSSR may be adjusted for an assumed minimum effect size. The minimum effect size assumed for BSSR may be lower than the effect size assumed for the sample size calculation in order to avoid underestimation of the within-group variance. The BSSR will be restricted such that the sample size may be unchanged or increased, but not reduced, as a result of the BSSR.

The methodology planned for this BSSR has been shown to generally control type 1 error (Kieser and Friede, 2003). Therefore, no adjustment will be made to the end-of-study analysis, considering an alpha of 0.05.

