6.2 CHANGES IN THE CONDUCT OF THE STUDY

The clinical trial CLI-06563AA1-02 started with the first obtained signed informed consent and enrolment on 18 December 2020 and was terminated in February 2022 due to a very low recruitment rate, that is 7 neonates instead of planned 57 in one year and after a long setup phase which was actually unexpected and far from the original estimates. It leads to a projection of another 6 years to complete the trial, that does not fit with acceptable timelines within the Chiesi portfolio development. Consequently, Chiesi has decided to early terminate the trial.

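### The blinded sample size re-assessment picks its babies by completion of treatment, which is the endpoint itself; on the day scale this lowers the pooled variance, by an amount that depends on accrual and on how 10-week withdrawals are counted

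*Protocol*

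**What the plan says.** Protocol section 12.3.8 sets the timing of the look: "A blinded sample size re-assessment (BSSR) will be performed when approximately 23-28 babies (40-50% of the planned sample size) have completed the treatment period". The data are the overall variance, for which "all completed patients (without knowledge or consideration of treatment arm) will be evaluated". The sample size may then rise or stay the same but may not fall. The section allows an adjustment for an assumed minimum effect, and lets that effect be smaller than the planned one so that the within-group variance is not underestimated. It has no rule for babies still on treatment at the look or for babies withdrawn at 10 weeks, and it does not say whether the variance is in days or on the log scale.

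The variance being checked comes from section 12.1, "assuming a common standard deviation of 15 days", for a 13-day difference with 80% power, a "two-sided significance level of 0.05" and "17 randomized to morphine and 34 randomized to CHF6563". The primary endpoint (sections 8.1 and 12.3.4) is the time from first to last dose, analysed on log-transformed hours. Section 4.4 withdraws babies who need more than 10 weeks of opioid therapy. Section 12.3.2 keeps them in the primary analysis with a value of at least 10 weeks.

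SAP v2.0, written after early termination, foresees no interim analysis (section 1.6). On recruitment, SAP section 6.2 reports "7 neonates instead of planned 57 in one year".

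**The concern.** Whether a baby is in the re-assessment depends on the value of the endpoint. When the 25th baby completes, those still on treatment are more often the long stayers, and their durations are missing from the variance. Babies withdrawn at 10 weeks, the longest of all, are missing too if they do not count as having completed. Both omissions cut the upper tail.

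The re-assessment can only raise N, so its one job is to detect a variance above plan. A sampling rule that lowers the variance works against that job. The permitted smaller assumed effect guards against subtracting too much for the treatment difference. It does not restore the durations that were never counted.

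**Working it through.** **1. The plan's own figure.** Inputs from section 12.1: difference 13 days, SD 15 days, two-sided 0.05, power 80%; 2:1 allocation from section 6.5. By the noncentral t, 16 + 32 babies give 79.1% power and 17 + 34 give 81.6%, so 51 evaluable is the smallest 2:1 design that reaches 80%. 51/0.9 = 56.7, hence 57 randomised. The trigger of 40-50% of 57 is 22.8-28.5, which matches 23-28. All reproduce.

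**2. Size of the selection effect.** Simulated trials had Poisson accrual, 2:1 arms, SD 15 days and durations capped at 70 days. The variance of the first 25 completers was divided by the variance of the first 25 randomised once all had finished. Assumed, because the documents do not give them: arm means from 15/28 to 25/38 days, lognormal or gamma shape, and the accrual pace.

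| Accrual | Completion order only | Over-10-week babies also left out |
|---|---|---|
| 7 a year | 0.98-0.99 | 0.83-0.89 |
| 57 a year | 0.86-0.93 | 0.75-0.83 |
| 114 a year | 0.72-0.83 | 0.65-0.75 (57 babies in 6 months, means 15/28 and 20/33) |

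Only 1-2% of babies exceeded 10 weeks in the runs with means 15/28 and 20/33, but they carry much of the tail. Their omission does not fade as accrual slows.

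**3. Log scale.** The completion-order ratio was 0.98-1.01 at 57 a year, and 0.94-1.04 over the wider set of settings. With over-10-week babies also left out and 57 babies accrued over 6 to 84 months, it was 0.92-1.03.

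**4. The between-arm term.** A variance pooled over 2:1 arms contains (2/3)(1/3) × 13² = (2/9) × 169 = 37.6 days² if the 13-day effect is real. So the pooled variance is 225 + 37.6 = 262.6 (SD 16.2), which is 16.7% above 225. Applying the ratios for 57 a year:

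- Completion order only, no adjustment: 262.6 × 0.86 = 225.8 and 262.6 × 0.93 = 244.2. Both are at or above 225. Simulated completer variances against the capped within-arm variance agree: 183 vs 175, 206 vs 188, 208 vs 202, 226 vs 207.
- Completion order only, full 13-day adjustment: 225.8 − 37.6 = 188.2 and 244.2 − 37.6 = 206.6, which are 0.84 and 0.92 of 225.
- Over-10-week babies also left out, no adjustment: 262.6 × 0.75 = 197.0 and 262.6 × 0.83 = 218.0, which are 12% and 3% below 225.

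At 114 a year, completion order alone gives 262.6 × 0.72 = 189.1 to 262.6 × 0.83 = 218.0, again below 225 without any adjustment.

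**5. What it could do to N.** Take a true SD of 18 days and let the ratio pass in full to the within-arm variance, that is, with no between-arm term to offset it. The normal approximation for the morphine arm is 1.5 × (1.960 + 0.842)² × SD²/13², rounded up and multiplied by 3.

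| Variance ratio | Evaluable N |
|---|---|
| 1.00 | 69 |
| 0.99 | 69 |
| 0.95 | 66 |
| 0.87 | 60 |
| 0.83 | 57 |
| 0.75 | 51 (no increase) |

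This approximation gives 48 rather than 51 at SD 15, so the rows should be compared with one another.

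**The case against.** Four points on the other side have force.

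- **Scale.** The primary model is on log hours. If the re-assessment used that scale, the completion-order bias would be a few per cent and could go either way. This stands. But section 12.3.8 names no scale, and the only planning SD is in days, so a check in days is the natural reading.
- **From variance to N.** A reader might infer that required N is low by the same 7-14%. The documents do not support that. Required N depends on the within-arm variance, the section 12.3.8 variance pools the arms, and the effect adjustment is optional. With the full effect present and nothing subtracted, the between-arm term covers the completion-order loss at 57 a year.
- **Accrual.** A reader might take 57 a year as the planned pace. The SAP phrase can mean that, or 7 recruited in a year out of a planned total of 57. The protocol states no rate, and 114 a year has no source in either document. At the observed pace completion order costs 1-2%.
- **Noise.** A variance from 25 babies has a sampling coefficient of variation of about √(2/24) = 29% even under normality, larger than the completion-order bias at 57 a year. That limits the practical gain, but it does not justify an avoidable error with a known direction.

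**Conclusion.** The concern holds in a conditional form. Section 12.3.8 chooses its data by the outcome, and on the day scale this lowers the pooled variance relative to a fixed cohort. The loss is about 7-14% at an assumed 57 babies a year and 1-2% at 7 a year. If over-10-week babies are not counted as completers, the total is about 17-25% and 11-17%. These sizes rest on the assumed means, shapes and accrual.

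N would be understated mainly when the true effect is smaller than 13 days, when an effect adjustment is subtracted, or when accrual is faster. Leaving out over-10-week babies adds to the shortfall. On the log scale no consistent downward bias from completion order was found.

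A reader might also infer that the rule harmed this trial. It did not: 7 babies were randomised, the trigger of 23 was not reached, and SAP v2.0 has no interim analysis. The point is a low-cost improvement for any reuse of the design.

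**What to change.** In section 12.3.8, define the re-assessment cohort by randomisation order: the first 25 (23-28) consecutively randomised babies, evaluated once each has finished treatment or been withdrawn. Enter withdrawals and over-10-week babies as section 12.3.2 does for the primary analysis. That rule uses a percentile taken regardless of arm, so the blind is kept.

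State the scale. Compute the variance in days, because the planning SD is in days. Use log duration only if a log-scale planning SD is also given, since otherwise there is nothing to compare it with.

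The cohort change is one sentence. The look waits at most about 10 weeks longer, until the last baby of the cohort reaches the end of treatment or the 70-day limit. A log-scale version would cost more, because the planning assumption in section 12.1 would have to be re-derived.
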